9.5. Emergency Unblinding of Treatment Assignment

In a medical emergency, if knowledge of the treatment assignment is necessary to determine optimal medical management of the participant, the procedure for emergency unblinding is provided in the Study Manual. This option may be used *only* if the participant's well-being requires the investigator to be aware of the participant's treatment assignment. If a participant's treatment assignment is unblinded, the sponsor or its designee must be notified immediately by telephone.

If an investigator, site personnel performing assessments, or participant is unblinded, the participant must be withdrawn from the study treatment, unless there are ethical reasons to have the participant remain on the study treatment. In these cases, the investigator must obtain specific approval from the sponsor's (or its designee's) medical monitor for the participant to continue in the study.

9.6. Pregnancy

Pregnancy, in and of itself, is not regarded as an AE unless there is suspicion that study drug may have interfered with the effectiveness of a contraceptive medication or method. When a pregnancy has been confirmed in a participant during maternal or paternal exposure to study drug, the following procedures should be followed in order to ensure safety:

- The study drug must be discontinued immediately (female participants only).
- The investigator must complete and submit the Incyte Clinical Trial Pregnancy Form to the sponsor or its designee within **24 hours** of learning of the pregnancy.

Data on fetal outcome are collected for regulatory reporting and drug safety evaluation. Follow-up should be conducted for each pregnancy to determine outcome, including spontaneous or voluntary termination, details of the birth, and the presence or absence of any birth defects, congenital abnormalities, or maternal and/or newborn complications, by following until the first well-baby visit. Pregnancy should be recorded on a Clinical Trial Pregnancy Form and reported by the investigator to the sponsor or its designee. Pregnancy follow-up information should be recorded on the same form and should include an assessment of the possible causal relationship to the sponsor's study drug to any pregnancy outcome, as well as follow-up to the first well-baby visit or the duration specified in local regulations, whichever is later. Refer to the Incyte Reference Guide for Completing the Clinical Trial Pregnancy Form.

Any SAE occurring during pregnancy of a study participant must be recorded on the Serious Adverse Event Report Form and submitted to the sponsor or designee.

Abnormal pregnancy outcomes (eg, spontaneous abortion, fetal death, stillbirth, congenital anomalies, or ectopic pregnancy) are considered SAEs (if occurring in the study participant) and must be reported as described in Section 9.4. If an abnormal pregnancy outcome is reported in a study participant's partner, the event should be reported to the sponsor on the Clinical Trial Pregnancy Form.

9.7. Warnings and Precautions

Special warnings or precautions for the study drug, derived from safety information collected by the sponsor or its designee, are presented in the IB. Additional safety information collected between IB updates will be communicated in the form of Investigator Notifications. Any important new safety information should be discussed with the participant during the study, as necessary. If new significant risks are identified, they will be added to the ICF.

9.8. Product Complaints

The sponsor collects product complaints on study drugs and drug delivery systems used in clinical studies in order to ensure the safety of study participants, monitor quality, and facilitate process and product improvements.

All product complaints associated with material packaged, labeled, and released by the sponsor or its designee will be reported to the sponsor. All product complaints associated with other study material will be reported directly to the respective manufacturer.

The investigator or his/her designee is responsible for reporting a complete description of the product complaint via email or other written communication to the sponsor contact or respective manufacturer as noted in the packaging information. Any AE associated with a product complaint should be recorded as described in Section 9.3.

If the investigator is asked to return the product for investigation, he/she will return a copy of the product complaint communication with the product.

9.9. Treatment of Overdose

For this study, any dose of study treatment greater than the assigned daily dose (depending on the participant's treatment assignment) within the same day will be considered an overdose. The Sponsor does not recommend specific treatment for an overdose.

In the event of an overdose, the investigator should:

- Contact the medical monitor immediately.
- Closely monitor the participant for any AE/SAE and laboratory abnormalities until INCB054707 can no longer be detected systemically (at least 3 days).
- Obtain a plasma sample for PK analysis within 3 days from the date of the last dose of study treatment if requested by the medical monitor (determined on a case-by-case basis).
- Document the quantity of the excess dose as well as the duration of the overdose in the eCRF.

Decisions regarding dose interruptions or modifications will be made by the investigator in consultation with the medical monitor based on the clinical evaluation of the participant.

There has been no clinical experience with overdose of INCB054707. Treatment of overdose should consist of general supportive measures.

10. STATISTICS

10.1. Sample Size Determination

10.2. Populations for Analysis

The populations for analysis are provided in Table 13.

I able 13: Populations for Analysis	able 13:	Populations for Analysis
-------------------------------------	----------	---------------------------------

Population	Description
ITT	The ITT population includes all randomized participants. Treatment groups for this population will be defined according to the treatment assignment at randomization.
РР	The PP population includes randomized participants who are considered to be sufficiently compliant with the Protocol.
Safety	The safety population includes all participants who received at least 1 dose of study drug. Treatment groups for this population will be determined according to the actual treatment the participant received on Day 1.

10.3. Level of Significance

10.4. Statistical Analyses

10.4.1. Primary Analysis

All other secondary variables will be summarized using descriptive statistics. For categorical measurements, summary statistics will include sample size, frequency, and percentages. For continuous measurements, summary statistics will include sample size, mean, median, standard deviation, minimum, and maximum. Summary statistics for continuous measures will be provided for baseline, the actual measurements at each visit, and the change and percentage change from baseline at each visit, if applicable.

10.4.3. Safety Analyses

Safety analyses will be conducted for the safety population. A TEAE is any AE either reported for the first time or worsening of a pre-existing event after first dose of study drug until the end of the safety follow-up period. Analysis of AEs will be limited to TEAEs, but data listings will include all AEs regardless of their timing to study drug administration. Adverse events will be tabulated by the MedDRA preferred term and system organ class. Severity of AEs will be based on the NCI CTCAE v5.0 using Grades 1 through 5.

The subset of AEs considered by the investigator to have a relationship to study drug will be considered to be treatment-related AEs. If the investigator does not specify the relationship of the AE to study drug, then the AE will be considered treatment-related. The incidence of AEs and treatment-related AEs will be tabulated.

The clinical laboratory data will be analyzed using summary statistics; no formal treatment group comparisons are planned. Laboratory test values outside the normal range will be assessed for

Version 2

severity based on the normal ranges for the clinical reference laboratory. The incidence of abnormal laboratory values and shift tables relative to baseline will be tabulated. Descriptive statistics and mean change from baseline will be determined for vital signs (ie, blood pressure, pulse, respiratory rate, and body temperature) at each assessment time. Descriptive statistics and mean change from baseline will be determined for each ECG parameters at each assessment time.

10.5. Interim Analysis

An interim analysis will not be performed for this study.

11. SUPPORTING DOCUMENTATION AND OPERATIONAL CONSIDERATIONS

11.1. Investigator Responsibilities

- The Protocol, Protocol amendments, ICF, IB, and other relevant documents (eg, advertisements) must be submitted to an IRB/IEC by the investigator and reviewed and approved by the IRB/IEC before the study is initiated.
- The investigator is responsible for ensuring that the safety reports provided by the sponsor are reviewed and processed in accordance with regulatory requirements, the policies and procedures established by the IRB/IEC, and institutional requirements.
- Any amendments to the Protocol will require approval from both Health Authorities and IRB/IEC before implementation of changes made to the study design, except for changes necessary to eliminate an immediate hazard to study participants.
- The investigator will be responsible for the following:
 - Providing written summaries of the status of the study to the IRB/IEC annually or more frequently in accordance with the requirements, policies, and procedures established by the IRB/IEC.
 - Notifying the IRB/IEC of SAEs or other significant safety findings as required by IRB/IEC procedures.
 - Providing oversight of the conduct of the study at the site and adherence to GCP, IRB/IEC requirements, institutional requirements, and applicable laws and country-specific regulations.
- Adhering to the Protocol as described in this document and agreeing that changes to the Protocol procedures, with the exception of medical emergencies, must be discussed and approved, first, by the sponsor or its designee and, second, by the IRB/IEC. Each investigator is responsible for enrolling participants who have met the specified eligibility criteria.
- Retaining records in accordance with all local, national, and regulatory laws but for a minimum period of at least 2 years after the last marketing application approval in an ICH region and until there are no pending or contemplated marketing applications in an ICH region, or if not approved, 2 years after the termination of the test article for investigation to ensure the availability of study documentation should it become necessary for the sponsor or a regulatory authority to review.
 - The investigator must not destroy any records associated with the study without receiving approval from the sponsor. The investigator must notify the sponsor or its designee in the event of accidental loss or destruction of any study records. If the investigator leaves the institution where the study was conducted, the sponsor or its designee must be contacted to arrange alternative record storage options.

 All eCRF data entered by the site (including audit trail), as well as computer hardware and software (for accessing the data), will be maintained or made available at the site in compliance with applicable record retention regulations. The sponsor will retain the original eCRF data and audit trail.

11.1.1. Identification of the Coordinating Principal Investigator

A coordinating principal investigator has been appointed by the Sponsor. As part of her responsibilities, the coordinating principal investigator will review the final CSR. Agreement with the final CSR will be documented by the dated signature of the coordinating principal investigator.

11.2. Data Management

Data management will be performed in a validated EDC system. The investigator will be provided with access to an EDC system so that an eCRF can be completed for each participant.

The site will be provided with eCRF completion guidelines for instructions on data entry in the eCRF. The study monitor will reference the Monitoring Plan in order to ensure that each issue identified is appropriately documented, reported, and resolved in a timely manner in accordance with the plan's requirements. Other data outside the EDC system required in the study conduct of the Protocol such as documents or results transmitted to the sponsor via a central laboratory or specialized technical vendors and, as designated by the sponsor, will have their own data flow management plans, study charters, **Burger and State Protocol** as applicable.

The sponsor (or designee) will be responsible for:

- Managing the integrity of the data and the quality of the conduct of the study, such as ensuring that study monitors perform ongoing source data verification to confirm that data entered into the eCRF by authorized site personnel are accurate, complete, and verifiable from source documents; that the safety and rights of participants are being protected; and that the study is being conducted in accordance with the currently approved Protocol and any other study agreements, ICH GCP, and all applicable regulatory requirements.
- Managing and reconciling the data generated, and/or collected including documents and results such as laboratory or imaging data analyzed centrally by a designated vendor of the sponsor.

The investigator will be responsible for:

- Recording, or ensuring the recording of, all relevant data relating to the study in the eCRF.
- Delivering, or ensuring the delivery of, all other results, documents, data, know-how, or formulas relating to the study to the sponsor or designee electronically and/or centrally (eg, laboratory data, imaging data, data), or as otherwise specified in the Protocol.
- Verifying that data entries are accurate and correct by physically or electronically signing the eCRF.

- Maintaining accurate documentation (source data) that supports the information entered in the eCRF, or sent to a central vendor designated by the sponsor, or as described in other study and data flow manuals.
 - Source documents provide evidence for the existence of the participant and substantiate the integrity of the data collected. Source documents are filed at the investigator's site.
 - Data entered in the eCRF that are transcribed from source documents must be consistent with the source documents or the discrepancies must be explained. The investigator may need to request previous medical records or transfer records, depending on the study. Current applicable medical records must be available.
- May have responsibility for sending participants' data, either as unique samples, or copies, or photographs, to be evaluated centrally or analyzed centrally, or both, by a qualified vendor designated by the sponsor.
- Permitting study-related monitoring, sponsor audits, IRB/IEC review, and regulatory inspections by providing direct access to source data and other relevant clinical study documents.
 - Monitoring: Qualified representatives of the sponsor or its designee, study monitors, will monitor the study according to a predetermined plan. The investigator must allow the study monitors to review any study materials and participant records at each monitoring visit.
 - Auditing: Qualified representatives of the sponsor or its designee may audit the clinical study site and study data to evaluate compliance with the Protocol, applicable local clinical study regulations, and overall study conduct. The investigator must allow the auditors to review original source records and study documentation for all participants.
 - Regulatory inspection: Regulatory authorities may conduct an inspection of the study and the site at any time during the development of an investigational product. The investigator and staff are expected to cooperate with the inspectors and allow access to all source documents supporting the eCRFs and other study-related documents. The investigator must immediately notify the sponsor when contacted by any regulatory authority for the purposes of conducting an inspection.

11.3. Data Privacy and Confidentiality of Study Records

The investigator and the sponsor or its designee must adhere to applicable data protection laws and regulations. The investigator and the sponsor or its designee are responsible for ensuring that sensitive personal information is handled in accordance with local data protection laws (including but not limited to HIPAA and GDPR) as applicable. Appropriate consent for collection, use and disclosure and/or transfer (if applicable) of personal information must be obtained in accordance with local data protection laws.

Participant names will not be supplied to the sponsor or its designee. Only the participant number will be recorded in the eCRF; if the participant's name appears on any other document

(eg, laboratory report), it must be obliterated on the copy of the document to be supplied to the sponsor or its designee. Study findings stored on a computer will be stored in accordance with appropriate technical and organizational measures as required by local data protection laws.

Records and documents, including signed ICFs, pertaining to the conduct of this study must be retained by the investigator for 30 years after study completion unless local regulations require otherwise. No records may be destroyed during the retention period without the written approval of the sponsor. No records may be transferred to another location or party without written notification to the sponsor.

11.4. Financial Disclosure

Before study initiation, all clinical investigators participating in clinical studies subject to FDA Regulation Title 21 CFR Part 54 – Financial Disclosure by Clinical Investigators (ie, "covered studies") are required to submit a completed Clinical Investigator Financial Disclosure form that sufficiently details any financial interests and arrangements that apply. For the purpose of this regulation, "clinical investigator" is defined as any investigator or subinvestigator who is directly involved in the treatment or evaluation of research participants, including the spouse and each dependent child of the clinical investigator or subinvestigator. These requirements apply to both US and foreign clinical investigators conducting covered clinical studies.

Any new clinical investigators added to the covered clinical study during its conduct must also submit a completed Investigator Financial Disclosure Form. During a covered clinical study, any changes to the financial information previously reported by a clinical investigator must be reported to the sponsor or its designee. At the conclusion of the covered clinical study, the clinical investigators will be reminded of their obligations. In the event that the clinical investigator is not reminded, they nevertheless will remain obligated to report to the sponsor or its designee any changes to the financial information previously reported, as well as any changes in their financial information for a period of 1 year after completion of the covered clinical study.

11.5. Publication Policy

By signing the study Protocol, the investigator and his/her institution agree that the results of the study may be used by the sponsor, Incyte Corporation (Incyte), for the purposes of national and international registration, publication, and information for medical and pharmaceutical professionals. Study results will be published in accordance with applicable local and national regulations. If necessary, the authorities will be notified of the investigator's name, address, qualifications, and extent of involvement. The terms regarding the publication of study results are contained in the agreement signed with the sponsor or its designee. A signed agreement will be retained by the sponsor or its designee.

The results of this study may be published or presented at scientific meetings. If this is foreseen, the investigator agrees to submit all manuscripts or abstracts to the sponsor before submission. This allows the sponsor to protect proprietary information and to provide comments.

The sponsor will comply with the requirements for publication of study results. In accordance with standard editorial and ethical practice, the sponsor will generally support publication of multicenter studies only in their entirety and not as individual site data. In this case, a coordinating investigator will be designated by mutual agreement.

Authorship will be determined in line with International Committee of Medical Journal Editors authorship requirements.

11.6. Study and Site Closure

The sponsor or designee reserves the right to close the study site or terminate the study at any time for any reason at the sole discretion of the sponsor. Study sites will be closed upon study completion. A study site is considered closed when all required documents and study supplies have been collected and a study-site closure visit has been performed.

The investigator may initiate study-site closure at any time, provided there is reasonable cause and sufficient notice is given in advance of the intended termination.

Reasons for the early closure of a study site by the sponsor or investigator may include but are not limited to:

- Failure of the investigator to comply with the Protocol, the requirements of the IRB/IEC or local health authorities, the sponsor's procedures, or GCP guidelines.
- Inadequate recruitment of participants by the investigator.
- Discontinuation of further study treatment development.

APPENDIX A. INFORMATION REGARDING EFFECTIVENESS OF CONTRACEPTIVE METHODS

For male participants in the study:

Male participants should use a condom from screening through 90 days after the end of systemic exposure. If the male participant has a partner that is of child-bearing potential, the partner should also use contraception through 90 days after the end of relevant systemic exposure. In addition, male participants must refrain from donating sperm from screening through 90 days after the end of relevant systemic exposure. Males who have had a vasectomy (assessed for surgical success) qualify as having met the requirement for a highly effective birth control method.

For female participants in the study:

The following methods that can achieve a failure rate of less than 1% per year when used consistently and correctly are considered as highly effective birth control methods:

- Combined (estrogen and progestogen containing) hormonal contraception associated with inhibition of ovulation^a
 - oral
 - intravaginal
 - transdermal
- Progestogen-only hormonal contraception associated with inhibition of ovulation^a
 - oral
 - injectable
 - implantable^b
- Intrauterine device^b
- Intrauterine hormone-releasing system^b
- Bilateral tubal occlusion^b
- Vasectomized partner^{bc}
- Sexual abstinence^d

Unacceptable birth control methods that result in a failure rate of more than 1% per year include:

- Progestogen-only oral hormonal contraception, where inhibition of ovulation is not the primary mode of action
- Male or female condom with or without spermicide^e
- Cap, diaphragm, or sponge with spermicide^e
- Tubal ligation

^a Hormonal contraception may be susceptible to interaction with the investigational medicinal product, which may reduce the efficacy of the contraception method.

^b Contraception methods that in the context of this guidance are considered to have low user dependency.

^c Vasectomized partner is a highly effective method of avoiding pregnancy provided that partner is the sole sexual partner of the woman of childbearing potential study participant and that the vasectomized partner has received medical assessment of the surgical success.

- ^d In the context of this guidance, sexual abstinence is considered a highly effective method only if defined as refraining from heterosexual intercourse during the entire period of risk associated with the study treatments. The reliability of sexual abstinence needs to be evaluated in relation to the duration of the clinical study and the preferred and usual lifestyle of the participant.
- ^e A combination of male condom with either cap, diaphragm, or sponge with spermicide (double barrier methods) are also considered unacceptable.

Source: Clinical Trials Facilitation and Coordination Group 2014.

Version 2

	Í	
- 1		
_		
•		

CONFIDENTIAL

i E			

CONFIDENTIAL

I.

ı.

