5.1. Inclusion Criteria

Participants are eligible to be included in the study only if all of the following criteria apply:

- 1. Men and women age 18 to 75 years inclusive at the time of signing the ICF.
- 2. HS disease duration of at least 3 months before screening.
- 3. Diagnosis of HS defined as:
 - a. A total of at least 5 inflammatory lesions (AN) at screening AND baseline AND
 - b. Inflammatory lesions present in at least 2 distinct anatomical areas
- 4. Willingness to avoid pregnancy or fathering children based on the criteria below.
 - a. Male participants with childbearing potential must agree to take appropriate precautions to avoid fathering children (with at least 99% certainty) from screening through 90 days after the last dose of study drug and must refrain from donating sperm during this period. Permitted methods that are at least 99% effective in preventing pregnancy (see Appendix A) should be communicated to the participants and their understanding confirmed.
 - b. Female participants with childbearing potential must have a negative serum pregnancy test at screening and must agree to take appropriate precautions to avoid pregnancy (with at least 99% certainty) from screening through safety follow-up. Permitted methods that are at least 99% effective in preventing pregnancy (see Appendix A) should be communicated to the participants and their understanding confirmed.
 - c. Female participants without childbearing potential (ie, surgically sterile with a hysterectomy and/or bilateral oophorectomy OR postmenopausal, defined as amenorrhea ≥ 12 months prior to screening), confirmed by FSH levels at screening, are eligible.
- 5. Participants agree NOT to use topical antiseptics (see Section 6.6.2) on the areas affected by HS lesions during the placebo-controlled 16-week treatment period.
- 6. For Germany only, participants must have a history of inadequate response or intolerance to an adequate course of oral antibiotics for treatment of HS, as assessed by the investigator through study participant interview and review of medical history.

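### Appendix A, the contraception list that criteria 4a and 4b rely on, gives two answers on tubal methods, does not show that the male measure reaches 99%, and ends the male precautions on a different date from criterion 4a

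*Protocol*

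**What the plan says.** Inclusion criterion 4 (Protocol Section 5.1) sets a threshold and points elsewhere for the methods. Men "must agree to take appropriate precautions to avoid fathering children (with at least 99% certainty" and women are held to the same level. Both sub-criteria then refer to Appendix A: "Permitted methods that are at least 99% effective in preventing pregnancy (see Appendix A". Criterion 4 itself names no contraceptive method.

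Appendix A has two parts.

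- **Men.** "Male participants should use a condom from screening through 90 days after the end of systemic exposure". A partner of childbearing potential is also to use contraception, with no effectiveness level given. A vasectomy checked for surgical success is the only male measure described as highly effective.
- **Women.** One list holds highly effective methods (failure below 1% per year) and includes "Bilateral tubal occlusion". A second list opens with "Unacceptable birth control methods that result in a failure rate of more than 1% per year include" and includes "Male or female condom with or without spermicide" and "Tubal ligation". Footnote e adds that a male condom combined with a cap, diaphragm or sponge is also unacceptable.

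The male time window appears twice. Criterion 4a runs "from screening through 90 days after the last dose of study drug and must refrain from donating sperm during this period". Appendix A counts the 90 days from the end of systemic exposure, for the condom, the partner's contraception and sperm donation.

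Sections 5.1 and 8.3.7.2 define non-childbearing potential by hysterectomy, bilateral oophorectomy or menopause. A tubal procedure is not among them.

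**The concern.** Appendix A is what turns the threshold in criterion 4 into a decision a site can make. If two of its entries fall on opposite sides of the threshold for what may be the same procedure, or if the measure given to men cannot be matched to the threshold, sites have to choose a reading. Section 5 rules out waivers and exemptions for eligibility, so there is no approved route round an unclear entry.

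About 50 sites and about 200 participants are planned. The rules stay in force well beyond enrolment. Planned dosing runs up to 16 + 36 + 48 = 100 weeks across the three treatment periods, and the male precautions continue after the last dose. At stake are consistent enrolment decisions and an even standard of pregnancy prevention across sites.

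**Working it through.** There is no trial figure to reproduce. The check sets the passages side by side, with one line of arithmetic to put the thresholds on the same scale.

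**Threshold.** Effectiveness of at least 99% means failure of at most 100% − 99% = 1%. Appendix A divides its lists at 1% per year. Criterion 4 gives no time base, so I assume the same annual basis. On that assumption the two use the same cut-off.

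**1. Tubal methods (both entries in the women's part of Appendix A)**

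| Entry | Rated failure per year | Meets 99%? |
|---|---|---|
| "Bilateral tubal occlusion" | below 1% | yes |
| "Tubal ligation" | above 1% | no |

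Neither term is defined and no distinction is drawn. That ligation is one way of occluding the tubes is ordinary medical meaning, which the documents do not state. A premenopausal woman with a tubal procedure, and without hysterectomy or bilateral oophorectomy, counts as of childbearing potential. If she relies on that procedure alone, criterion 4b is met or not met according to the label the site records.

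**2. Men without a vasectomy (criterion 4a against Appendix A)**

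| Component of the male measure | Effectiveness in the documents |
|---|---|
| Condom | above 1% failure per year; the only rating given, in the women's list |
| Partner's contraception | no level stated |
| Both together | cannot be scored |

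The condom alone falls on the wrong side of 1%. The combination cannot be compared with 1% because one component has no stated level. A condom with a partner's diaphragm would satisfy the wording of the male paragraph, yet footnote e calls that combination unacceptable in the women's part. The documents therefore do not show that the male measure meets criterion 4a.

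**3. End of the male precautions**

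Let L be the date of last dose and E the time from last dose to the end of systemic exposure.

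- Criterion 4a: end date = L + 90 days.
- Appendix A: end date = L + E + 90 days.
- Gap = (L + E + 90) − (L + 90) = E.

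The documents give no value of E after normal dosing, so the gap cannot be quantified. The disagreement also covers sperm donation, which both passages regulate. In addition, Appendix A speaks of systemic exposure in one sentence and relevant systemic exposure in two others, without saying whether these differ.

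**The case against.** The strongest reply is that Appendix A is written in two parts and should be read that way. The list that refuses the condom stands under the women's heading. When a man's partner is of childbearing potential, his section asks for two measures, a condom and partner contraception. A reader might infer that the condom is prescribed and refused for the same person, and the documents do not support that. A man whose partner uses a method from the highly effective list presents no clear difficulty. This stands, and it limits the male point to a missing standard for the partner's method and for the combination.

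It can also be said that criterion 4 tests willingness. A woman with a tubal procedure who agrees to another listed method qualifies on either reading. That stands too: the tubal conflict matters only for a woman who relies on the procedure. Nor is it a conflict between criterion 4 and Appendix A, since criterion 4 names no method. It lies inside the appendix. The other listed female methods, and vasectomy for men, can be applied as written, so it would be too much to say that sites have no workable rule.

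The summary of changes in Appendix D records that Appendix A was updated in Amendment 1. The detail is not visible in the copy reviewed, so it cannot show which tubal entry was intended.

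**Conclusion.** Wrong as written, in three limited respects: two undefined tubal entries on opposite sides of 1%, a male measure not shown to reach the level in criterion 4a, and two end dates for the male precautions. The tubal point rests on the ordinary medical meaning of ligation. The male point rests on reading the women's-list rating as applying to the condom generally, since no other rating is given.

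Four stronger readings are tempting but unsupported.

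- **A count of affected participants.** The documents give no sex split, menopausal status or contraceptive mix, so none can be derived.
- **A gap of at least 3 days between the end dates.** That figure in Section 9.9 is a minimum monitoring time after an overdose. It is not the length of exposure after a last normal dose.
- **Treatment for 104 weeks.** Dosing ends by Week 100, and Week 104 is the safety follow-up visit.
- **Damage to the per-protocol analysis.** SAP Section 5.3.2 leaves exclusions to the clinical team's judgement of sufficient compliance and does not name contraception. That population serves only a sensitivity analysis (SAP Section 7.4.3).

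The consequence is uneven eligibility decisions and pregnancy precautions between sites. Sample size, power and type I error are not affected.

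**What to change.** Reconcile criteria 4a and 4b with Appendix A in the next protocol amendment, and send sites a clarification letter. The revised text should give:

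1. one status for tubal methods, or a stated distinction between the two terms;
2. one effectiveness standard for male participants and for their partners' method, worded so that it agrees with the 99% level in criterion 4a;
3. one end date for the male precautions, including sperm donation, used in both places.

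Which status, standard and date to adopt is for the sponsor's clinical and safety functions to decide. The cost is wording in Section 5.1 and Appendix A plus one letter to sites. No procedure, visit or participant is added, and the SAP does not change.
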